## **6.5.5 Management of Specific Adverse Events or Adverse Drug Reactions**

Any Grade 4 ADRs require treatment discontinuation except for single laboratory values out of normal range that are unlikely related to study treatment as assessed by the Investigator, do not have any clinical correlate, and resolve within 7 days with adequate medical management.

Any Grade  $\geq 3$  AEs and irAEs require treatment discontinuation with exception of any of ADRs mentioned in Section [6.2.3](#) and [6.2.4](#) in the DLT criteria.

#### 6.5.5.1 Infusion-Related Reactions

CCI

CCI

#### 6.5.5.2 Severe Hypersensitivity Reactions and Flu-Like Symptoms

If hypersensitivity reaction occurs, the subject must be treated according to the best available medical practice. A complete guideline for the emergency treatment of anaphylactic reactions according to the Working Group of the Resuscitation Council (United Kingdom) can be found at <https://www.resus.org.uk/pages/reaction.pdf> (UK Resuscitation Council). Subjects should be instructed to report any delayed reactions to the investigator immediately.

**A. Symptoms**

- Impaired airway
- Decreased oxygen saturation (< 92%)
- Confusion
- Lethargy
- Hypotension
- Pale/clammy skin
- Cyanosis.

[figure not shown]
**B. Management**

- Epinephrine injection and dexamethasone infusion
- Subject should be placed on monitor immediately
- Alert intensive care unit for possible transfer if required

[figure not shown]
**CCI**

**CCI**

**Figure 2** Assessment and Initial Management of Tumor Lysis Syndrome

TLS = tumor lysis syndrome.

### 6.5.5.3 Immune-Related Adverse Events

Since inhibition of PD-L1 stimulates the immune system, irAEs may occur. Treatment of irAEs is mainly dependent upon severity (NCI-CTCAE grade):

- Grade 1 to 2: treat symptomatically or with moderate dose steroids, more frequent monitoring
- Grade 1 to 2 (persistent): manage similar to high grade AE (Grade 3 to 4)
- Grade 3 to 4: treat with high dose corticosteroids.

Treatment of irAEs should follow guidelines set forth in [Table 9](#).

**Table 9 Management of Immune-Related Adverse Events of CCI  
M4112 as Single Agent CCI**

Gastrointestinal irAEs		
Severity of Diarrhea/Colitis (NCI-CTCAE 4.03)	Initial Management	Follow-up Management
Grade 1 Diarrhea: < 4 stools/day over Baseline Colitis: asymptomatic	CCI M4112 therapy Symptomatic treatment (eg, loperamide)	Close monitoring for worsening symptoms Educate subject to report worsening immediately If worsens: Treat as Grade 2, 3, or 4
Grade 2 Diarrhea: 4 to 6 stools per day over Baseline; iv fluids indicated < 24 h; not interfering with ADL Colitis: abdominal pain; blood in stool	Delay CCI, or M4112 therapy Symptomatic treatment	If improves to Grade 1: Resume CCI or M4112 therapy  If persists > 5 to 7 days or recurs: Treat as Grade 3 to 4
Grade 3 to 4 Diarrhea (Grade 3): ≥ 7 stools per day over Baseline; incontinence; iv fluids ≥ 24 h; interfering with ADL Colitis (Grade 3): severe abdominal pain, medical intervention indicated, peritoneal signs Grade 4: life-threatening, perforation	Withhold CCI CCI M4112 therapy for Grade 3 Permanently discontinue CCI M4112 therapy for Grade 4 or recurrent Grade 3. 1.0 to 2.0 mg/kg/day prednisone or equivalent Add prophylactic antibiotics for opportunistic infections Consider lower endoscopy	If improves: Continue steroids until Grade 1, then taper over at least 1 month, resume CCI therapy following steroids taper (for initial Grade 3).  If worsens, persists > 3 to 5 days, or recurs after improvement: Add infliximab 5 mg/kg (if no contraindication), Note: Infliximab should not be used in cases of perforation or sepsis Permanently discontinue IMP

Dermatological irAEs		
Grade of Rash (NCI-CTCAE 4.03)	Initial Management	Follow-up Management
Grade 1 to 2 Covering ≤ 30% body surface area	Continue CCI [REDACTED] M4112 therapy Symptomatic therapy (for example, antihistamines, topical steroids)	If persists > 1 to 2 weeks or recurs: Withhold CCI [REDACTED] M4112 therapy Consider skin biopsy CCI [REDACTED] [REDACTED] If worsens: Treat as Grade 3 to 4
Grade 3 to 4 Covering > 30% body surface area; life threatening consequences	Withhold CCI [REDACTED] M4112 therapy for Grade 3. Permanently discontinue for Grade 4 or recurrent Grade 3 Consider skin biopsy Dermatology consult 1.0 to 2.0 mg/kg/day prednisone or equivalent	If improves to Grade 1: Taper steroids over at least 1 month and add prophylactic antibiotics for opportunistic infections CCI [REDACTED]

Pulmonary irAEs		
Grade of Pneumonitis (NCI-CTCAE 4.03)	Initial Management	Follow-up Management
Grade 1 Radiographic changes only	Consider withholding CCI [REDACTED], or M4112 therapy Monitor for symptoms every 2 to 3 days Consider Pulmonary and Infectious Disease consults	Re-assess at least every 3 weeks If worsens: Treat as Grade 2 or Grade 3 to 4
Grade 2 Mild to moderate new symptoms	Withhold CCI [REDACTED] M4112 therapy Pulmonary and Infectious Disease consults Monitor symptoms daily, consider hospitalization 1.0 to 2.0 mg/kg/day prednisone or equivalent Consider bronchoscopy, lung biopsy	Re-assess every 1 to 3 days If improves: When symptoms return to near Baseline, taper steroids over at least 1 month, consider prophylactic antibiotics for opportunistic infections, and then resume CCI [REDACTED] M4112 therapy following steroids taper If not improving after 2 weeks or worsening: Treat as Grade 3 to 4
Grade 3 to 4 Grade 3: Severe new symptoms;	Permanently discontinue CCI [REDACTED] M4112 therapy	If improves to Baseline: Taper steroids over at least 6 weeks

Pulmonary irAEs		
Grade of Pneumonitis (NCI-CTCAE 4.03)	Initial Management	Follow-up Management
New/worsening hypoxia; Grade 4: life-threatening	Hospitalize Pulmonary and Infectious Disease consults 1.0 to 2.0 mg/kg/day prednisone equivalent Add prophylactic antibiotics for opportunistic infections Consider bronchoscopy, lung biopsy	If not improving after 48 h or worsening: Add additional immunosuppression (for example, infliximab, cyclophosphamide, iv immunoglobulin, or mycophenolate mofetil)

Hepatic irAEs		
Grade of Liver Test Elevation (NCI-CTCAE 4.03)	Initial Management	Follow-up Management
Grade 1 Grade 1 AST or ALT > ULN to 3.0 x ULN and/or total bilirubin > ULN to 1.5 x ULN	Continue CCI [REDACTED] [REDACTED] M4112 therapy	Continue liver function monitoring If worsens: Treat as Grade 2 or 3 to 4
Grade 2 AST or ALT > 3.0 to $\leq$ 5 x ULN and/or total bilirubin > 1.5 to $\leq$ 3 x ULN	Withhold CCI [REDACTED] [REDACTED] M4112 therapy Increase frequency of monitoring to every 1 to 2 days 1.0 to 2.0 mg/kg/day prednisone or equivalent. Add prophylactic antibiotics for opportunistic infections Consult gastroenterologist/ hepatologist Consider obtaining MRI/CT scan of liver and liver biopsy if clinically warranted	If returns to Baseline: Taper steroids over at least 1 month, consider prophylactic antibiotics for opportunistic infections, and resume CCI [REDACTED] M4112 therapy following steroids taper. If worsens: Treat as Grade 3-4.
Grade 3 to 4 AST or ALT > 5 x ULN and/or total bilirubin > 3 x ULN	Discontinue CCI [REDACTED] [REDACTED] M4112 therapy Increase frequency of monitoring to every 1 to 2 days 1.0 to 2.0 mg/kg/day methylprednisolone iv or iv equivalent Add prophylactic antibiotics for opportunistic infections Consult gastroenterologist Consider obtaining MRI/CT scan of liver and liver biopsy if clinically warranted (for	If returns to Grade 2: Taper steroids over at least 1 month If does not improve in > 3 to 5 days, worsens or rebounds: Add mycophenolate mofetil 1 gram (g) twice daily If no response within an additional 3 to 5 days, consider other immunosuppressants per local guidelines

Hepatic irAEs		
Grade of Liver Test Elevation (NCI-CTCAE 4.03)	Initial Management	Follow-up Management
	study sites in Germany, only MRI is to be used)	

Renal irAEs		
Grade of Creatinine Increased (NCI-CTCAE 4.03)	Initial Management	Follow-up Management
Grade 1 Creatinine increased > ULN to 1.5 x ULN	Continue CCI [REDACTED] M4112 therapy	Continue renal function monitoring If worsens: Treat as Grade 2 to 3 or 4
Grade 2 Creatinine increased > 1.5 to 6 x ULN	Withhold CCI [REDACTED] M4112 therapy Increase frequency of monitoring to every 3 days 1.0 to 2.0 mg/kg/day prednisone or equivalent. Add prophylactic antibiotics for opportunistic infections Consider renal biopsy	If returns to Baseline: Taper steroids over at least 1 month, and resume CCI [REDACTED] M4112 therapy following steroids taper. If worsens: Treat as Grade 4.
Grade 3 to 4 Creatinine increased > 6 x ULN	Permanently discontinue CCI [REDACTED] M4112 therapy Monitor creatinine daily 1.0 to 2.0 mg/kg/day prednisone or equivalent. Add prophylactic antibiotics for opportunistic infections Consider renal biopsy Nephrology consult	If returns to baseline: Taper steroids over at least 1 month,

Cardiac irAES		
Myocarditis	Initial Management	Follow-up Management
New onset of cardiac signs or symptoms and/or new laboratory CCI [REDACTED] or cardiac imaging abnormalities suggestive of myocarditis.	Withhold CCI [REDACTED] [REDACTED] M4112 therapy Hospitalize In the presence of life threatening cardiac decompensation, consider transfer to a facility experienced in advanced heart failure and arrhythmia management Cardiology consult to	If symptoms improve and immune-mediated etiology is ruled out, re-start CCI [REDACTED] CCI [REDACTED] M4112 therapy. If symptoms do not improve/worsen, viral myocarditis is excluded, and immune-mediated etiology is suspected or confirmed following cardiology consult, manage as immune-mediated myocarditis.

Cardiac irAES		
Myocarditis	Initial Management	Follow-up Management
	
establish etiology and rule-out immune-mediated myocarditis.
 
Guideline based supportive treatment as per cardiology consult.*
 
Consider myocardial biopsy if recommended per cardiology consult.
	
Immune-mediated myocarditis	
Permanently discontinue CCI M4112 therapy.
 
Guideline based supportive treatment as appropriate as per cardiology consult.*
 
1.0 to 2.0 mg/kg/day prednisone or equivalent.
	
Once improving, taper steroids over at least 1 month and add prophylactic antibiotics for opportunistic infections.
 
If no improvement or worsening, consider additional immunosuppressants (eg, azathioprine, cyclosporine A)

\*Local guidelines, or eg. ESC or AHA guidelines  
 ESC guidelines website: <https://www.escardio.org/Guidelines/Clinical-Practice-Guidelines>  
 AHA guidelines website: <http://professional.heart.org/professional/GuidelinesStatements/searchresults.jsp?q=&y=&t=1001>

Endocrine irAEs		
Endocrine Disorder	Initial Management	Follow-up Management
Grade 1 or Grade 2 endocrinopathies (hypothyroidism, hyperthyroidism, adrenal insufficiency, type I diabetes mellitus)		Continue hormone replacement/ suppression and monitoring of endocrine function as appropriate
Grade 3 or Grade 4 endocrinopathies (hypothyroidism, hyperthyroidism, adrenal insufficiency, type I diabetes mellitus)	
Withhold CCI M4112 therapy
 
Consider hospitalization
 
Endocrinology consult
 
Start thyroid hormone replacement therapy (for hypothyroidism), anti-thyroid treatment (for hyperthyroidism), corticosteroids (for adrenal insufficiency), or insulin (for type I diabetes mellitus) as appropriate.
	
Resume CCI M4112 therapy once symptoms and/or laboratory tests improve (with or without hormone replacement/suppression).
 
Continue hormone replacement/ suppression and monitoring of endocrine function as appropriate

[figure not shown]
Endocrine irAEs		
Endocrine Disorder	Initial Management	Follow-up Management
	Rule-out secondary endocrinopathies (ie, hypopituitarism/hypophysitis)	
Hypopituitarism/Hypophysitis (secondary endocrinopathies)	
If secondary thyroid and/or adrenal insufficiency is confirmed (ie, subnormal serum Free T4 with inappropriately low TSH and/or low serum cortisol with inappropriately low ACTH) :
 
 
Refer to endocrinologist for dynamic testing as indicated and measurement of other hormones (FSH, LH, GH/IGF-1, PRL, testosterone in men, estrogens in women)
 
Start hormone replacement/ suppressive therapy as appropriate
 
Perform pituitary MRI and visual field examination as indicated
 
 
If hypophysitis confirmed:
 
 
Continue CCI [REDACTED] M4112 therapy if mild or moderate symptoms with normal MRI. Repeat the MRI in 1 month
 
Withhold CCI [REDACTED] 4112 therapy if severe symptoms or life-threatening symptoms of hypophysitis and/or abnormal MRI. Consider hospitalization. Initiate high-dose corticosteroids (1 to 2 mg/kg/day methylprednisolone iv or equivalent) followed by corticosteroids taper during at least 1 month.
 
	
Resume CCI [REDACTED] M4112 therapy once symptoms and hormone tests improve (with or without hormone replacement).
 
In addition, for hypophysitis with abnormal MRI, resume CCI [REDACTED] M4112 therapy only once shrinkage of the pituitary gland on MRI scan is documented.
 
Continue hormone replacement/ suppression therapy as appropriate.

Other irAEs (not described above)		
Grade of other irAEs (NCI-CTCAE 4.03)	Grade of other irAEs (NCI-CTCAE 4.03)	Grade of other irAEs (NCI-CTCAE 4.03)
	Initial Management	Follow-up Management
Grade 2 or Grade 3 clinical signs or symptoms suggestive of a potential irAE	Withhold CCI [REDACTED] M4112 therapy pending clinical investigation	If irAE is ruled out, manage as appropriate according to the diagnosis and consider re-starting CCI [REDACTED] M4112 therapy If irAE is confirmed, treat as Grade 2 or 3 irAE
Grade 2 irAE or first occurrence of Grade 3 irAE	Withhold CCI [REDACTED] M4112 therapy 1.0 to 2.0 mg/kg/day prednisone or equivalent Add prophylactic antibiotics for opportunistic infections Specialty consult as appropriate	If improves to Grade 1: Taper steroids over at least 1 month and resume CCI [REDACTED] M4112 therapy following steroids taper
Recurrence of same Grade 3 irAEs	Permanently discontinue CCI [REDACTED] M4112 therapy 1.0 to 2.0 mg/kg/day prednisone or equivalent Add prophylactic antibiotics for opportunistic infections Specialty consult as appropriate	If improves to Grade 1: Taper steroids over at least 1 month
Grade 4	Permanently discontinue CCI [REDACTED] M4112 therapy 1.0 to 2.0 mg/kg/day prednisone or equivalent and/or other immunosuppressant as needed Add prophylactic antibiotics for opportunistic infections Specialty consult.	If improves to Grade 1: Taper steroids over at least 1 month
Requirement for 10 mg per day or greater prednisone or equivalent for more than 12 weeks for reasons other than hormonal replacement for adrenal insufficiency Persistent Grade 2 or 3 irAE lasting 12 weeks or longer	Permanently discontinue CCI [REDACTED] M4112 therapy Specialty consult	

ALT = alanine aminotransferase; AST = aspartate aminotransferase; CT = computed tomography; irAE = immune-related adverse event; MRI = magnetic resonance imaging; NCI-CTCAE 4.03 = National Cancer Institute-Common Terminology Criteria for Adverse Events Version 4.03; T4 = thyroxine; TSH = thyroid-stimulating hormone; ULN = upper limit of normal.

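### In the renal block of Table 9, the row labels put Grade 3 with Grade 4, while the follow-up pointers group it with Grade 2

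*Protocol*

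**What the plan says.** Protocol Section 6.5.5.3 makes treatment of immune-related adverse events (irAEs) depend mainly on NCI-CTCAE grade and refers sites to Table 9. In the renal block, the first column heading names the scale: "Grade of Creatinine Increased (NCI-CTCAE 4.03". The block has three rows.

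- **Grade 1**: creatinine above ULN and up to 1.5 x ULN. Treatment continues. Follow-up: "If worsens: Treat as Grade 2 to 3 or 4".
- **Grade 2**: "Creatinine increased > 1.5 to 6 x ULN". Treatment is withheld. Monitoring: "Increase frequency of monitoring to every 3 days". On recovery: "If returns to Baseline: Taper steroids over at least 1 month, and resume" treatment. Otherwise: "If worsens: Treat as Grade 4".
- **Grade 3 to 4**: "Creatinine increased > 6 x ULN". Treatment is permanently discontinued. Monitoring: "Monitor creatinine daily". A nephrology consult is added, and there is no provision to resume.

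The steroid dose, the prophylactic antibiotics and the suggestion to consider a renal biopsy are the same in the Grade 2 and Grade 3 to 4 rows.

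**The concern.** The block groups Grade 3 in two ways. By label it sits with Grade 4. The Grade 1 pointer joins it to Grade 2 and sets Grade 4 apart, and the Grade 2 pointer goes straight to Grade 4 without naming Grade 3. No row is labelled Grade 2 to 3, and none is labelled Grade 4 alone, so neither pointer names a row that exists as labelled.

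The two candidate rows differ in the initial drug action, in how often creatinine is checked and in whether a nephrologist is consulted. In a first-in-human study with few subjects per dose level, two sites could manage the same Grade 3 renal event differently and each cite the table.

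**Working it through.** No arithmetic applies. The check sets labels, bands and pointers side by side and then looks elsewhere in the protocol for a rule that settles the matter.

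| Item in Table 9 | How it groups the grades |
|---|---|
| Renal row labels | 1; 2; 3 to 4 |
| Renal Grade 1 pointer | 2 to 3; 4 |
| Renal Grade 2 pointer | next step is 4; Grade 3 not named |
| Hepatic row labels | 1; 2; 3 to 4 |
| Hepatic pointers | 2; 3 to 4 |
| Pulmonary row labels | 1; 2; 3 to 4 |
| Pulmonary pointers | 2; 3 to 4 |

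1. **Within the renal block.** The two pointers agree with each other (1; 2 to 3; 4) and disagree with the labels (1; 2; 3 to 4). That looks like more than one misplaced word.

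2. **Against other blocks.** The hepatic and pulmonary blocks carry the same three labels, and their pointers match them. The mismatch is therefore not a convention of the table.

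3. **The bands.** The printed ranges are above ULN to 1.5, above 1.5 to 6, and above 6 x ULN. They meet without gap or overlap, so any raised creatinine falls in exactly one row. The conflict arises only when a site starts from the grade, as Section 6.5.5.3 and the column heading direct.

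4. **Which side is wrong.** This turns on where 6 x ULN falls on the named scale, and the documents do not reproduce that scale.
   - If 6 x ULN separates Grade 3 from Grade 4, bands and pointers agree and the labels are wrong.
   - If it separates Grade 2 from Grade 3, bands and labels agree and the pointers are wrong.
   - If it does neither, the bands need correcting too.

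5. **Other rules.** Section 6.5.5 requires discontinuation for irAEs of Grade 3 or higher, but makes exceptions by reference to Sections 6.2.3 and 6.2.4. Section 6.2.3 lets some subjects interrupt and continue at a reduced dose after the DLT period. Section 5.5.1 lists irAEs of Grade 3 or higher as a reason for withdrawal, but only as defined in Section 6.2.4. Both general rules lean toward the label reading; neither corrects the pointers.

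6. **Scope.** A DLT in Cycle 1 already ends protocol therapy under Sections 5.5.1 and 6.2.4. The ambiguity therefore matters mainly for Grade 3 renal events after Cycle 1.

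**The case against.** The strongest reply is that the table still gives a usable answer. Only one row names Grade 3, the bands put every value in one place, and the Grade 2 pointer, followed literally, also leads to the bottom row. On this view the problem is one loosely worded phrase in the Grade 1 row.

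Much of this stands. A site that reads off the multiple of ULN meets no conflict, and the Grade 2 pointer does not by itself send anyone to the wrong row. What does not fall away is that the protocol directs management by grade, and the Grade 1 pointer can be read as sending Grade 3 to the withhold row. Redaction does not explain it, because the labels, bands and pointers are all visible.

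A reader might go further and infer that the protocol keeps subjects with Grade 3 renal toxicity on treatment, or that both pointers misdirect care. The documents do not support either. The label and the general rules lean toward discontinuation, and Section 6.2.3 ends treatment after any delay of more than 2 weeks, which limits how far withholding could lead to resumption. That limit is a separate matter, since it applies to Grade 2 renal cases whatever the pointers say.

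A reader might also infer that the labels must be right and the pointers simply need editing. That is not supported either: the pointers are consistent with each other, and editing them first could fix the error in place.

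**Conclusion.** The renal block is wrong as written, because its labels and pointers cannot both be right about Grade 3. The point is minor. It concerns Grade 3 renal irAEs managed by grade, mainly after Cycle 1. What is at stake is withholding versus permanent discontinuation as the first drug action, creatinine every 3 days versus daily, and the absence or presence of a nephrology consult. No endpoint, DLT criterion, sample size or planned analysis is affected.

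The conclusion rests on the visible text alone. It makes no assumption about the external creatinine cut-points, so it does not say which grouping was intended.

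**What to change.** First check the two creatinine bands (above 1.5 to 6, and above 6 x ULN) against the NCI-CTCAE 4.03 grades named in the column heading. Then make label, band and pointer agree:

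- If the bands follow a split of Grade 2 to 3 and Grade 4, as both pointers suggest, relabel the lower two rows Grade 2 to 3 and Grade 4, and keep the pointers.
- Otherwise keep the labels and change the pointers to Grade 2 or 3 to 4 (Grade 1 row) and Grade 3 to 4 (Grade 2 row), as in the hepatic block. Correct the 6 x ULN cut as well if the check shows that it does not separate Grade 2 from Grade 3.

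The cost is one check against a published scale and a few words in one table. The statistical sections and the DLT definition stay as they are.

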## 6.6 Packaging and Labeling of the Investigational Medicinal Product

CCI

[figure not shown]
### M4112

M4112 will be packaged in child resistant and tamper sealed wallets. Each wallet will contain 1 blister with 4 tablets of 25 mg or 200 mg M4112 tablets.

All IMPs will be packaged and labeled in accordance with all applicable regulatory requirements and Good Manufacturing Practice Guidelines. All IMPs will be shipped in suitable transport containers according to each IMP's storage and shipping conditions. Shipments are monitored with temperature control devices.

## 6.7 Preparation, Handling, and Storage of the Investigational Medicinal Product

CCI

CCI

## M4112

M4112 tablets are ready for use and do not require any preparation,

M4112 must be stored at < 25°C and must not be frozen until use, with a temperature log maintained daily. All medication boxes supplied to each study site must be stored carefully, safely, and separately from other drugs.

M4112 must not be used for any purpose other than the study. The administration of M4112 to subjects who have not been enrolled into the study is not covered by the study insurance.

Any unused M4112 should be discarded in biohazard waste disposal with final disposal by accepted local and national standards of incineration.

Storage, handling, preparation, and disposal of IMP should be according to local institutional guidelines.

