## **6.8                   Investigational Medicinal Product Accountability**

The Investigator is responsible for ensuring accountability for study drugs, including reconciliation of drugs and maintenance of drug records.

Upon receipt of study drugs, the Investigator (or designee) will check for accurate delivery and acknowledge receipt by signing (or initialing) and dating the documentation provided by the Sponsor and returning it to the Sponsor. A copy will be retained for the Investigator File

The dispensing of the study drugs will be carefully recorded on the appropriate drug accountability forms provided by the Sponsor and an accurate accounting will be available for verification by the Sponsor's Monitor at each monitoring visit.

Study drugs accountability records will include:

- Confirmation of study drugs delivery to the study site;
- The inventory at the site of study drugs provided by the Sponsor and prepared at the site
- The use of each dose by each subject
- The return to the Sponsor or alternative disposition of unused study drugs
- Dates, quantities, batch numbers, expiry dates and (for study drugs prepared at the site) formulation, as well as the subjects' study numbers.

The Investigator should maintain records that adequately document:

- That the subjects were provided the doses specified by the clinical study protocol/amendment(s)
- That all study drugs provided by the Sponsor was fully reconciled.

Unused study drugs must not be discarded or used for any purpose other than the present study. Any study drug that has been dispensed to a subject must not be redispensed to a different subject.

The Sponsor's Monitor will periodically collect the study drugs accountability forms and will check all returns (both unused and used containers) before arranging or authorizing their destruction by the study site.

At the conclusion or termination of this study, study site personnel and the Clinical Study Monitor will conduct a final product supply inventory on the Investigational Drug Accountability Forms and all unused containers will be destroyed. Instructions for destruction of product will be provided to the site. The Clinical Study Monitor will be supplied with a copy for filing of the

Investigational Drug Accountability Forms. This documentation must contain a record of clinical supplies used, unused, and destroyed and shall include information on:

- All administered units
- All unused units
- All destroyed units (during the study)

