## 6.9 Assessment of Investigational Medicinal Product Compliance

In this study, subjects will receive study treatment at the investigational site. Well-trained medical staff will monitor and perform the on-site study drug administration. Subjects will be instructed by the Investigator/designee regarding off-site self-administration of M4112, and compliance checks performed at all study visits. The information of each study drug administration (date and dose of study drug) will be recorded on the eCRF. On evenings preceding PK sampling time of drug intake will also be recorded. Subjects will be provided with predosing drug diaries for Days 8 and 15 of Cycle 1 and Day 1 of Cycle 2. The Investigator will ensure that the information entered into the eCRF regarding drug administration is accurate for each subject. Any reason for noncompliance should be documented.

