## 13 Treatment Compliance and Exposure

All dosing calculations and summaries will be based on the "M4112 Administration Details" CRF page. The Safety Analysis Set will be used for these analyses.

Handling of missing data:

- If the total actual dose is missing, the planned dose level as entered in the CRF will be used.
- In case the last medication end date is incomplete, the date of M4112 administration will be taken from the "M4112 Termination" page.

The duration of therapy (in weeks) is defined as:

$$\text{Duration} = [(\text{date of last dose} - \text{date of first dose}) + 1] / 7$$

The cumulative dose of M4112 (in mg) is defined as:

$$\text{Cumulative dose (mg)} = [(\text{tablets dispensed}) - (\text{tablets returned})] * \text{dose level (mg)}$$

(Summed over all dose levels taken by the subject, if dosing changes occurred.)

Dose intensity (mg/week) will be calculated as follows:

$$\text{Dose intensity (mg/week)} = \left( \frac{\text{Total cumulative dose of M4112 (mg)}}{\text{Duration of therapy (weeks)}} \right)$$

The relative dose intensity (%) is defined as the dose intensity divided by the planned cumulative dose per cycle, calculated as follows:

$$\text{Relative dose intensity (\%)} = \left( \frac{\text{Total cumulative dose of M4112 (mg)}}{\text{Total planned dose of M4112 (mg)}} \right) * 100\%$$

The following summary tables by dose group and overall will be provided:

- Duration of therapy (weeks)
- Total number of doses taken overall
- Cumulative dose (mg)
- Dose intensity (mg/week)
- Relative dose intensity (%)
- Dose adjustments and missed doses

A listing of treatment exposure and compliance will also be created to summarize the relevant information for each subject:

- Cycle and day in cycle
- Date and time of administration
- Actual dose

- Whether dose has been adjusted, and if yes, reason why
- Reason for no dose (if applicable)

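### Protocol 6.7 and 6.8 conflict on discarding unused M4112, and the SAP's exposure formula counts dispensed tablets that are discarded or lost without a logged return as taken

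*Protocol*

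**What the plan says.** Protocol 6.7, under M4112, gives a disposal instruction: "Any unused M4112 should be discarded in biohazard waste disposal with final disposal by accepted local and national standards of incineration". It does not mention return, counting or reconciliation, and it refers disposal to local institutional guidelines.

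Protocol 6.8 covers all study drugs and reads differently: "Unused study drugs must not be discarded or used for any purpose other than the present study". It adds that the sponsor's monitor "will check all returns (both unused and used containers) before arranging or authorizing their destruction by the study site". The accountability records must show, among other items, "The return to the Sponsor or alternative disposition of unused study drugs".

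SAP Section 13 (Treatment Compliance and Exposure) opens by basing all dosing calculations on the M4112 Administration Details CRF page. It then defines cumulative dose as tablets dispensed minus tablets returned, multiplied by the dose level in mg. Dose intensity is that cumulative dose divided by weeks of therapy. For the third measure the text says "The relative dose intensity (%) is defined as the dose intensity divided by the planned cumulative dose per cycle, calculated as follows", but the displayed formula is total cumulative dose over total planned dose. SAP Section 18.1 flags an overdose deviation by program when relative dose intensity is 1.10 or more.

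**The concern.** A site that follows 6.7 literally may dispose of leftover tablets before anyone counts them. A site that follows 6.8 may not. The SAP formula has only two places for a tablet: returned or taken. A dispensed tablet that goes into biohazard waste, or is lost, without a logged return falls into the second.

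The error runs one way, upward, and is largest where most tablets are left over. Dose intensity and relative dose intensity are tabulated by dose group in a study whose primary objective is safety, tolerability and the RP2D. An inflated figure would make a dose level look better taken than it was. Because the overdose check uses the same ratio, uncounted surplus tablets could also create false deviations.

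**Working it through.** The documents state no dose-intensity figure, so there is nothing to reproduce. The check applies the SAP formulas directly.

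**Inputs**
- Tablet strengths of 25 mg and 200 mg, four tablets per wallet (Protocol 6.6).
- BID dosing in 28-day cycles, with 600 mg BID and 200 mg BID among the planned levels (Protocol 5.1).
- Exposure formulas (SAP 13) and overdose threshold of 1.10 (SAP 18.1).
- Assumed, because the documents give no counts: the tablets left over, the share discarded uncounted, the number dispensed, and doses made up of 200 mg tablets. Missed days are taken to fall inside the cycle, so duration stays at 4 weeks. Tablets are converted to mg by tablet strength. Relative dose intensity uses the displayed formula.

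**General form.** Let D be tablets dispensed, R returned, T taken, and U dispensed but neither taken nor logged as returned. Then D − R = T + U. The formula reports T + U where the truth is T, so cumulative dose is inflated by (T + U)/T = 1 + U/T. Duration and planned dose do not depend on U, so dose intensity and relative dose intensity inflate by the same factor.

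**Illustration, 600 mg BID.** Each dose is 600/200 = 3 tablets, so 6 a day and 6 × 28 = 168 per cycle. Missing 8 days leaves 8 × 6 = 48 tablets; T = 120.

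| Of 48 left over, discarded uncounted (U) | Counted as taken | Cumulative dose (mg) | Dose intensity (mg/week) | Relative dose intensity | Factor |
|---|---|---|---|---|---|
| 0 (true value) | 120 | 24,000 | 6,000 | 120/168 = 71.4% | 1.00 |
| 24 | 144 | 28,800 | 7,200 | 144/168 = 85.7% | 1.20 |
| 48 | 168 | 33,600 | 8,400 | 168/168 = 100% | 1.40 |

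**Overdose check, 200 mg BID.** One 200 mg tablet per dose gives 56 planned per cycle. Suppose all 56 are taken and surplus tablets were also dispensed.
- One spare wallet discarded uncounted: 60/56 = 107.1%, no flag.
- Six surplus tablets: 62/56 = 1.107, which is flagged. Five give 61/56 = 1.089, which is not.
- Two spare wallets: 64/56 = 114.3%, flagged.

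The true value is 100% in each case, so these flags would be false.

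**Where there is no inflation.** Stock never dispensed is not in D. Tablets returned, counted and then destroyed are in R. In both cases U = 0 and the formula is right.

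**A separate unit problem.** The formula multiplies tablets by dose level, not tablet strength. Read literally, with dose level as the per-administration dose, a fully taken cycle at 600 mg BID gives 168 × 600 = 100,800 mg against 168 × 200 = 33,600 mg, with nothing discarded. The illustration sets this aside, but the formula needs correcting wherever it is kept.

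**The case against.** The strongest reply is that 6.7 and 6.8 describe two steps of one process: 6.8 says what must happen before destruction, and 6.7 says how destruction is done. Section 6.8 itself provides for destruction by the site and for all unused containers to be destroyed at the end. It also requires full reconciliation and records of administered, unused and destroyed units. On that reading, a tablet discarded uncounted is already a breach of 6.8, and the SAP already names the administration CRF page as its source.

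Much of this stands. It rules out the broader inference that discarded tablets in general inflate exposure: only tablets dispensed and then discarded or lost without a logged return do so.

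A reader might also infer that no other record could correct the count, since Protocol 6.9 says "Subjects will be provided with predosing drug diaries for Days 8 and 15 of Cycle 1 and Day 1 of Cycle 2" and mentions no diary for other days. The documents do not support that. Section 6.9 also requires the date and dose of each administration on the eCRF, compliance checks at every visit, and documented reasons for noncompliance. A dose without a diary is not a dose without a record.

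Three things survive the reply. Section 6.7 does not state the sequence. The formula makes no use of the alternative-disposition record that 6.8 requires. SAP 13 gives two sources for the same quantity, the CRF administrations and a tablet balance, without saying which governs.

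**Conclusion.** The point holds in limited form. Protocol 6.7 and 6.8 conflict as worded and must be reconciled. The SAP formula counts every dispensed, unreturned tablet as taken, which biases three exposure measures upward by 1 + U/T and can falsely trip the overdose check. The size of the bias in this trial is unknown, because the documents give no count of discarded or lost tablets. The factors of 1.20 and 1.40 are illustrations that rest on assumed leftovers, assumed uncounted discard and conversion by tablet strength.

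A reader might go further and infer that DLT evaluability is affected, because it turns on missed total daily doses. The documents do not support this: neither the protocol rule nor the SAP's DLT set definition refers to tablet reconciliation. The exposure measures do not enter the Bayesian DLT model.

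Severity is minor. Exposure summaries are not among the listed endpoints, and all analyses are descriptive.

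**What to change.** 1. **Protocol 6.7.** Replace the discard sentence with one that follows 6.8: unused M4112 is returned to the site, counted, logged, and destroyed only after the monitor has reconciled it.
2. **SAP 13.** Compute cumulative dose from the administrations recorded on the CRF page already named as the source. Keep dispensed minus returned only as a cross-check where the return count is complete, with tablets converted by tablet strength. Make the wording of relative dose intensity match its formula.
3. **SAP 13, missing data.** The section fills a missing total actual dose with the planned dose level. Once administrations govern, that rule can also push exposure upward where the dose was missed or reduced, so report how often it is used.

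The cost is one protocol sentence and a few SAP sentences, with no new data collection. The diary does not need extending. The SAP was written after the decision to stop the study early, so the SAP edit is the one that can still protect the reported figures, even if the protocol sentence is changed too late to alter site practice.
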